Week 1/day 1: An investigator will place one AFU in the bedroom of each participant's apartment. Each AFU will be set to either "active mode" (i.e., a HEPA filter inside) or "sham mode" (i.e., no HEPA filter inside) in **randomized double-blind fashion**. We have documented that both modes exhibit similar noise and identical appearance. This will be accomplished by having a different (unblinded) investigator set the AFU modes offsite beforehand – so that neither the on-site investigator nor the participants will be aware of the settings during all study blocks. This offsite unblinded investigator will be the only team member aware of the randomization order. For the **placebo intervention**: both AFUs will be set to "sham mode". The AFUs will remain running in the same mode for the entire 4-week study block.

Week 1/days 2-4: Participants will be asked to sleep every night in their own apartment and measure their blood pressure using a home BP device we provide just prior to going to bed and upon waking up. At the end of the visit on day 4, participants will have heart rate variability determined with a holter monitor for 6 minutes and blood pressure measured using the BPTru device. Subjects will be fitted with 2 portable devices: an ambulatory BP monitor and a personal PM2.5 monitor. At all times during the 24-hour period, they will wear the PM monitor or have it near them (e.g., on bedside stand while sleeping). We have demonstrated that these devices can be worn together for 24 hours without excessive burden^{38,40}. During this period, participants will be instructed not to exercise.

Week 1/day 5: Upon arrival the personal monitoring devices will be collected.

Weeks 2-3: Participants will undertake their usual activities (except for overnight travel restrictions).

Week 4: Study visit days 2-5 will be repeated as during week 1.

Visit day 5 is completed and prior to eating or taking medications, participants will have blood drawn in the study room by an investigator. An investigator will then remove the AFUs from participants' apartments.

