AFU intervention: We have carefully designed this study to accommodate the needs and limitations of the volunteer subjects and minimize changes and burdens on their lifestyle by incorporating noninvasive daily home BP testing while also assuring detection of outcome-exposure associations based on our previous studies. As described above in the Progress Report section, despite the fact that the RAPIDS protocol did not restrict subjects' activities (e.g., window opening), we were able to reduce personal PM2.5 exposure and observe improved CV health outcomes. Thus, we will maintain the same protocol and study real-world exposure to the extent possible. Apartment central air conditioning and heating can be used without limitations. Participants will record in activity logs any period in which windows are opened. We will employ the same commercially available AFU brand (Holmes) proven in RAPIDS to effectively reduce indoor and personal PM2.5 exposures and lower BP among participants³⁰. For the "gold standard" comparison (2-room AFU use), we will follow the same deployment protocol successfully used in RAPIDS30 and supported by EPA guidance and expert scientific opinions⁷³⁻⁷⁶. At 8AM Monday (week 1, visit day 1) of each study block, a blinded onsite investigator will place AFUs in each participant's residence. One AFU each will be placed in both the bedroom and main living room. Each AFU will be set to the randomized mode ("active" or "sham") per the description in prior sections in a *randomized double-blind fashion* by a different offsite investigator beforehand so that neither the onsite investigator nor the participant will be aware of the settings (the HEPA filter is not visible from the outside). In both rooms the AFU will be a Holmes HAP8650B-NU-1, designed for spaces up to 310 square feet. Under the "active" mode, the AFU will be fitted with a new "true HEPA" filter (Holmes HAPF600TCS), validated to remove 99.97% of particles at 0.3 μm in size⁷³. Ultrafine (10-100 nm) particles (e.g., from traffic) and larger particles (e.g., coarse PM) are typically filtered even more effectively by HEPA filters⁷³⁻⁷⁶. Under the "sham" mode, a HEPA filter will not be installed in the AFU and there will be no significant removal of PM2.5. Each AFU will be fitted with a cumulative power consumption meter (Kill-A-Watt EZ) to verify continuous operation at the correct fan speed setting for the entire intervention period. The low noise level of the AFUs will be indistinguishable between active and sham

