
Table 1: List of Study Endpoints

Health Endpoints	Endpoint designation
Unattended automated systolic BP 4-day average (Tues-Fri) in weeks 1 and 4	Primary study outcome (Aims 1a, 2a/2b) Study is a priori powered for this endpoint
24-hour BP levels & aortic hemodynamics	Secondary endpoints (Aims 1c & 2d)
Insulin sensitivity (HOMA-IR)	Secondary endpoint (Aims 1c & 2d)
Adrenal steroid panel (blood)	Secondary mechanistic endpoints (Aims 3a/3b)
Exposure Endpoints	
24-hr personal PM _{2.5} (filter-gravimetric mass)	Primary exposure outcome (Aims 1b, 2c)
Daily indoor PM _{2.5}	Primary exposure outcome (Aims 1b)
Black carbon, hourly personal PM _{2.5} levels	Secondary exposure endpoints

modes. In RAPIDS, no participant complained or required the AFU to be stopped due to noise³⁰. The AFUs will run in the same blinded mode continuously for the entire 4-week block. During the washout periods, the offsite investigator will

remove or install the HEPA filters in the AFUs prior to starting the next block. The HEPA filters are rated to be effective for the entire 8 weeks of active usage and will not need to be replaced.

Protocols for cardiometabolic health endpoints

Home BP: This BP measurement will be the primary outcome (Table 1). The **rationale** is that high BP is a well-established predictor of CV risk⁶⁸⁻⁷¹, the leading risk factor for global mortality³, increases due to short-term PM2.5 exposure^{5-8,36-56}, and was shown by our RAPIDS study³⁰ to be reduced by AFUs. Unattended automated BP more accurately reflects 24-hour BP, is less impacted by variability and the white coat effect and is superior to the standard technique as a predictor of hypertensive complications⁷¹. The repeat-measured morning BP average using the BpTRU device was the primary outcome in RAPIDS³⁰, thus it is important to use this same method in this renewal project.

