PM2.5 monitoring: Continue with in-room (PurpleAir) monitoring per original study design for full 4 weeks of both study blocks. We will use personal-PM2.5 monitoring (pDR-1500); however, it will not occur during week-1 but only at end of week-4 for both study blocks (once per study block).

Air filter intervention: No changes. We will continue the protocol using portable air cleaners (PACs) in the bedroom without change for 4 weeks in active and sham conditions.

Study flow: All study devices (home BP monitors, pDR-1500 personal PM2.5 monitors, PurpleAir in-room PM monitors, PACs) will be cleaned and sterilized (per COVID-19 protocols) before they are provided to each subject. The devices will be provided to the subjects without any contact with the research team members. At the appropriate time in the protocol, the subjects will be notified by phone and the equipment and instructions for usage and set up will be dropped off for the participants at their doorway at a pre-arranged time.

Advanced Covid Restrictions:

Study staff will not enter residences or have any personal contact with any subject or potential subject. In the event of elevated Covid concerns the study staff will not enter hallways and will deliver equipment to the front doorway to Carpenter Place. In cases where the subject agrees, the study staff may enter apartments to set up the equipment. Our 2021 experience has proven that some subjects have physical limitations to moving the equipment (frailty, walkers and small apartments, etc)

Study Protocol:

Recruitment: Advertisements and recruitment will be done without personal contact. We will provide fliers for recruitment with a contact number to the research coordinator for interested residents. The staff members who work and are present at Carpenter Place will post the fliers in Carpenter place bulletin boards and notify residents that the study is active and has been modified to be simpler and to eliminate any contact with the research team. Advertisements will continue in the residential newsletter.

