Week-4/Day-5: On the final day of each study block, the coordinator will contact the subject. They subject will be instructed to place the equipment (randomized PAC, PurpleAir, pDR-1500, and home BP device) in the bin with wheels and bring it to the front lobby of Carpenter Place. The coordinator will then pick-up the equipment.

Data collection: The coordinator will collect/data-base the time-stamped home BP readings from week-1 and week-4. They will download all the time/date-stamped PM2.5 data from the PurpleAir and data-base the results. They will also download and data-base the 24-hour personal PM2.5 exposure results from the pDR-1500.

As-needed visits: During the study period, the subject can call and schedule an as-needed telephone or video visit with the research coordinator at any time to discuss any study-related issues or problems.

Washout-period. During the washout period the coordinator will clean and sterilize all the equipment. They will change the PAC to the alternative randomized blinded mode (active vs sham). They will call the subject and schedule the timeline for Block-2 (week-1/visit-1).

Block-2: This block will proceed exactly as block-1, except the subject will be provided the alternative randomized (blinded) PAC intervention.

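### The modified washout procedure has the coordinator switch the air cleaner between active and sham, a step the main protocol reserves for a separate unblinded offsite investigator

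*Combined protocol and SAP*

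**What the plan says.** The main protocol describes the blinding under Block 1, Week 1/day 1. An unblinded investigator sets the modes away from the site, "so that neither the on-site investigator nor the participants will be aware of the settings during all study blocks". It adds: "This offsite unblinded investigator will be the only team member aware of the randomization order". The AFU intervention paragraph repeats the separation, calls the person who places the units blinded, and notes that "the HEPA filter is not visible from the outside". It also covers the switch between blocks: "During the washout periods, the offsite investigator will" "remove or install the HEPA filters in the AFUs prior to starting the next block".

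The Protocol Modifications section, which now governs conduct, states "Air filter intervention: No changes". Its Study Flow paragraph keeps the original design apart from removing face-to-face contact and simplifying the procedures. Its Washout-period paragraph opens with "During the washout period the coordinator will clean and sterilize all the equipment" and continues "They will change the PAC to the alternative randomized blinded mode (active vs sham". The next sentence has the same subject telephone the participant to schedule block 2.

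**The concern.** The two parts of the current document give the mode switch to different people. The difference matters because of the coordinator's other duties in the modified protocol. The coordinator schedules block 2, gives the week-4 reminders, contacts the participant on the last day of the block, takes as-needed calls, collects the equipment, and downloads and enters the home BP and PM2.5 data. Home BP is the BP measure that remains after the BpTRU and ambulatory measurements were removed.

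Two things are at stake. The first is an indirect route to bias. The participant chooses the fan setting according to what is tolerable, and a caller who knows the mode could influence that choice or the participant's general engagement. The second, and firmer, is reporting. If the washout paragraph was followed, the blinding described in the main protocol did not hold for the staff member closest to participants and data.

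**Working it through.** The plan gives no figure to reproduce on this point, so the check is mainly a comparison of texts, followed by simple counts.

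**Who makes the switch**

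- Main protocol, Block 1 and AFU intervention: the offsite unblinded investigator, including the filter change in washout.
- Modifications, Washout-period: three consecutive tasks (clean, switch the mode, call the participant). Only the coordinator is named. The third task is plainly the coordinator's, so the second reads the same way.
- Nothing in the modifications transfers the unblinded role or says that the coordinator holds it. The mode-setter for block 1 is not named either; that sentence is passive.

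**What the person making the switch learns**

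Sham means that no HEPA filter is installed. The filter is hidden only while the unit stays closed, and no pre-coded sealed units are described. Opening the unit to add or remove the filter reveals the block-2 mode. With two modes and two periods, block 1 must have been the other mode, so the full sequence is known.

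**Possible readings**

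1. The coordinator has taken over the unblinded role. The participant-facing role is then no longer blind.
2. The coordinator and the offsite investigator both know the order. The statement that one person alone knows it is then untrue.
3. The offsite investigator still makes the switch and the paragraph is loosely drafted. The current text is then wrong.

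All three need a correction.

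**Scheduled coordinator contacts after the switch** (modified protocol)

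- Block-2 scheduling call: 1
- Week-4 reminders (BP and personal PM, possibly one call): 1 to 2
- Contact on week-4/day-5: 1
- Total: 1 + (1 to 2) + 1 = 3 to 4 per participant; 3 × 50 = 150 and 4 × 50 = 200 over 50 completers. As-needed visits come on top, with no stated cap.
- Before personal monitoring starts on week-4/day-4: 1 + (1 to 2) = 2 to 3. The remaining contact falls on the last BP day.

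**Cost of separating the roles again**

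- One-way unit transfers relative to the washout paragraph: 2 in washout (out and back) plus 0 to 2 before block 1, giving 2 to 4 per participant. Range: 2 × 50 = 100 to 4 × 55 = 220, using 50 completers and 55 enrolled.
- Time available: the schedule table labels block 2 as weeks 6 to 9. With the first Monday as day 0, pick-up on Friday of week 4 is day 25 and drop-off on Monday of week 6 is day 35. 35 − 25 = 10 calendar days, with 5 working days in week 5.

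**The case against.** The strongest case against is that this is a drafting ambiguity with little consequence.

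- *The double-blind label.* The main protocol defines blinding for the onsite investigator and the participants and openly allows one unblinded person. No text says that the coordinator cannot be that person. It is fair that the label never covered all staff. But the AFU intervention paragraph describes the participant-facing role as blinded, so merging the two roles breaks the intended separation.
- *The statement of no changes.* The sentence after it concerns device, room and duration, so it may not speak to staffing. That stands. It only means that the washout paragraph may replace the earlier rule, in which case the coordinator is unblinded without the plan saying so.
- *Location.* The offsite description refers to where the modes are set, and the coordinator could also work offsite after pick-up. Also, staff in general deliver the air cleaner; the coordinator delivers the personal monitor and collects the equipment. The objection to a merged role therefore rests on participant contact and data handling.
- *Bias.* The calls have stated administrative purposes. Participants stay masked and take triplicate readings on a device that stores them with time stamps, alongside a log. A Data Coordinating Center reviews data quality. The power meter in the main protocol, if retained, would limit the fan-setting route. All of this stands, and it is why no bias is claimed in mm Hg.
- *Residual clues.* The coordinator would still download the in-room PM2.5 data. In the earlier trial, living-room levels were 17.5 µg/m³ on sham and 7.0 µg/m³ on high-efficiency filtration, so readings could suggest the mode. This is a real limit of the fix, but no reason for the coordinator to open the unit.

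**Conclusion.** The point holds and should be fixed: the procedure is wrong as written. Confidence is high for the textual conflict. The size of any bias cannot be derived from the documents, and the route is indirect. The 150 to 200 scheduled contacts measure opportunity, not effect. The conclusion assumes that the coordinator is the subject of the washout sentences, that the coordinator and the offsite investigator are different people, and that switching the mode means opening the unit. The documents support the first by grammar and the third by the definition of sham. They are silent on the second, and if one person holds both roles, the loss of a blinded participant-facing role remains. Actual practice is unknown, and no other staff member is shown to be unblinded.

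**What to change.** Reconcile the Block 1 and AFU intervention paragraphs of the main protocol with the Air filter intervention and Washout-period paragraphs of the modifications. One or two sentences suffice:

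- The existing offsite unblinded investigator sets the mode for both blocks and returns a closed unit labelled with the participant ID.
- No one with participant contact or access to BP data opens the unit.
- Any cleaning inside the unit moves to the offsite investigator. The coordinator cleans the closed unit and the other equipment and makes the calls as now.

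The modifications refer to experience in 2021, so some participants may already have crossed over. For them, record who switched the mode, and describe staff blinding in the report accordingly.

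If the offsite role is still filled, no new staff are needed. Relative to the washout paragraph, the change adds 100 to 220 one-way transfers in total, fewer if batched, to be fitted with cleaning into the 10-day window. Relative to the main protocol it adds none. The retrospective log is short. Endpoints, sample size and participant burden are unchanged. The fix removes direct knowledge of the mode but not hints from the PM2.5 data.
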